Center Destination (Mexico)	School of Optometry Clinic, National Autonomous University (UNAM)
Number of Centers	Single Center
Patient Follow-up	
Subjects enrolled in this study will be followed up after the lens dispensing session:
 
 • Post dispensing follow-up at 1 hour for each study lens pair
Primary Endpoint	High contrast visual acuity
Secondary Endpoints	Lens fitting characteristics, subjective ratings, preference, and ocular response.

Table of Contents

1	Introduction	6
2	Study Objective	6
3	Study Hypothesis	6
3.1	Study Hypothesis	6
4	Study Design	6
5	Investigational Sites	6
5.1	Number of Sites	6
5.2	Investigator Recruitment	7
6	Ethics Review / Statement of Compliance	7
6.1	Relevant Standards / Guidelines	7
6.2	Institutional Review Board	7
6.3	Clinical Trial Registration	7
6.4	Informed Consent	7
7	Potential Risks and Benefits to Human Subjects	8
8	Materials and Methods	8
8.1	Participants	8
	Inclusion criteria	8
8.2	Study Materials	9
8.2.1	Contact lens	9
8.2.2	Contact Lens care	10
8.2.3	Storage of Study Medications/Treatments	10
8.2.4	Clinical Supply Inventory	10
8.2.5	Disposal of Consumables	10
8.2.6	Masking and Control of Study Materials	10
8.2.7	Ordering and Accountability of Study Materials	10
8.3	Visit Schedule and Procedures	11
8.3.1	Visit 1 after dispensing (Fit lenses / Evaluate [e.g. P1])	11
8.3.2	Visit 2 after 1 hour (Assess lenses / Study exit)	12
9	Adverse Event Reporting	12
9.1	Adverse Response Definitions	12
9.2	Procedures for Adverse Events	14
9.3	Reporting Adverse Events	15
9.4	Discontinuation from the Study	15
10	Statistical Analysis	15
10.1	Statistical analysis	15

11 Data Quality Assurance	16
11.1 Study monitoring.....	16
11.2 Record keeping	16
11.3 Record retention	16
11.4 Data Entry / Data Management	16
11.5 Confidentiality.....	16
11.6 Publication.....	16
12 Study Costs and Subject Compensation.....	17
13 Appendixes.....	18

1 Introduction

Biomedics XC is part of an older generation of a hydrogel contact lens portfolio from CooperVision which will be discontinued soon.

Therefore, CooperVision is interested in switching wearers of the Biomedics XC brand into the Proclear hydrogel or Clariti® elite silicone hydrogel contact lenses. A non-dispensing fitting study is proposed to evaluate the clinical performance of these lenses.

2 Study Objective

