3.1 Study Hypothesis

- Null hypothesis (H₀): There is no difference in high contrast visual acuity, lens fitting characteristics, and subjective assessments between lens types.
- Alternative hypothesis (H₁): There is a difference in high contrast visual acuity, lens fitting characteristics and subjective assessments between lens types.

4 Study Design

This is a 40-subject, double masked, randomized, bilateral, non-dispensing fitting trial comparing hydrogel and silicone hydrogel lens materials. It is anticipated that this study will involve 2 visits for each lens pair, as follows: Visits: V1 (lens dispensing), V2 (1 hour post lens settling). Each subject will be randomized to wear each pair bilaterally in a series of three short fitting comparisons.

5 Investigational Sites

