8.3 Visit Schedule and Procedures

This will be a randomized, double masked, bilateral, non-dispensing fitting study. Participants will be examined at two different points over the course of one day, V1 (lens dispensing), V2 (1 hour post lens settling). They will wear three different pairs of lenses in randomized fashion. Anterior ocular health examination will be performed at baseline without the use of fluorescein*.

Next, the study lenses will be dispensed and fit evaluated. After 1 hour of wear, lens fit assessments will be collected and the lenses removed. Anterior ocular health examination will be performed with fluorescein and the subjects exited from the study. This same procedure will be repeated at a different day for each lens pair.

** Fluorescein will not be used before lens dispensing to prevent potential eye discomfort that could influence subjective comfort ratings after lens fitting and settling. However, fluorescein will be instilled at the 1 hour visit upon lens removal.*

The following outline identifies the two study visits and the general procedures, (Appendix 5), to be conducted at each visit for each day of the study and recorded in the case report forms (Appendix 6):

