8.3.1 Visit 1 after dispensing (Fit lenses / Evaluate [e.g. P1])

- Explanation of the study
- Sign informed consent form
- Anterior ocular health examination (Slit lamp without fluorescein)
- Insert lenses from pair # 1
- Visual acuity
 - High contrast, monocular logMAR
 - High contrast, binocular log MAR
- Subjective assessments
 - Handling on insertion (0 -100 scale). **Subject to insert study lenses and rate handling.**
 - Comfort on insertion (0 -100 scale)
 - Burning/stinging (0 – 100 scale)
 - Comfort preference (right vs. left)
- Lens fit assessment
 - Lens centration (optimum, decentration acceptable, decentration unacceptable)
 - Corneal coverage [Y/N]
 - Post blink movement (0-5 Likert scale)
 - Lens tightness on push-up test (0% - 100% in 5% steps)
 - Overall fit acceptance (0 – 4) and reason if Grade 2 or less.
 - Investigator's fit preference

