8.3.2 Visit 2 after 1 hour (Assess lenses / Study exit)

- Subjective assessments
 - Comfort on insertion (0 -100 scale)
 - Comfort preference (right vs. left)
 - Handling on removal (0 -100 scale)
- Lens fit assessment
 - Lens centration (optimum, decentration acceptable, decentration unacceptable)
 - Corneal coverage [Y/N]
 - Post blink movement (0-5 Likert scale)
 - Lens tightness on push-up test (0% - 100% in 5% steps)
 - Overall fit acceptance (0 – 4) and reason if Grade 2 or less.
 - Investigator's fit preference
 - Lens removal by subject
- Anterior ocular health examination with fluorescein
- Study exit form must be completed
- Subjects will be required to come to the clinic on a separate day to be fitted with the other study lenses.
- The same procedure as section 8.3.1 and 8.3.2 will be performed for the rest of the lens pairs.

9 Adverse Event Reporting

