10.1 Statistical analysis

Summary statistics will be produced, (e.g. mean, standard deviation), by the principal investigator ([name]). Differences between lenses will be compared using Paired t-tests. Paired t-tests /analysis of variance for normal (interval/continuous) data, Wilcoxon's signed ranks test for non-normal (ordinal) data, chi-squares test for nominal data. A Chi-Square test will be used to evaluate lens preference questions.

A sample size of 33 subjects was calculated which provides 80% power to detect a difference of half a line in logMAR high contrast visual acuity (HCVA). The critical alpha level for statistical significance will be set at $p \leq 0.05$, with adjustment for multiple comparisons. All participants who are evaluated in the study will be used in the analysis. In the event of missing data, individual numbers points will be excluded in the analysis and not extrapolated from the collected data.

11 Data Quality Assurance

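### Section 10.1 gives nominal data an unqualified chi-square although the same subjects wear all three lenses; run in its ordinary form on corneal coverage, its error rate is wrong, in a direction that depends on the unit of analysis

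*Combined protocol and SAP*

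**What the plan says.** The design is within-subject. Section 4 states: "Each subject will be randomized to wear each pair bilaterally in a series of three short fitting comparisons". Section 8.3 confirms it ("They will wear three different pairs of lenses in randomized fashion"), and section 8.3.2 repeats the visit procedures for each pair: "The same procedure as section 8.3.1 and 8.3.2 will be performed for the rest of the lens pairs".

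The fit assessment at both visits (sections 8.3.1 and 8.3.2) includes the yes/no item "Corneal coverage [Y/N". The synopsis lists the secondary endpoints as "Lens fitting characteristics, subjective ratings, preference, and ocular response", so coverage is a secondary fit item.

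On tests, section 10.1 says "Differences between lenses will be compared using Paired t-tests" and then allocates methods by data type, ending with "signed ranks test for non-normal (ordinal) data, chi-squares test for nominal data". A separate sentence covers preference: "A Chi-Square test will be used to evaluate lens preference questions". No matched test for nominal data is named. Nothing says whether coverage is analysed by eye or by subject, or how two eyes are combined. Section 10.1 promises an adjustment for multiple comparisons without naming the method. It also says that missing points are left out rather than imputed.

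**The concern.** The methods named for continuous and ordinal data use each subject as his or her own control. The method named for nominal data does not, unless the analyst chooses a matched form. A lens-by-category chi-square on coverage assumes independent rows, but the rows are the same people under three lenses and possibly two eyes of each person. Its standard error is then wrong.

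If each subject gives one value per lens, the likely loss is power: a real coverage difference between lenses could be missed. If each eye is a row, the two eyes' agreement under the same lens pushes the other way, and a false difference becomes possible. The plan permits either reading, so the choice could be made after the data are seen.

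The concern is confined to corneal coverage. Centration is graded in ordered categories and falls under the signed-rank test. A chi-square on a single preference answer per subject is sound.

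**Working it through.** **Plan's own figure.** Section 10.1 gives no figure for coverage. Its sample size of 33 concerns visual acuity and has no bearing here.

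**Inputs.** From the documents: three lenses, 40 subjects (synopsis), level 0.05. Assumed, because the documents give none: coverage rates, within-subject correlations and variance shares. The adjusted pairwise level is taken as 0.05/3 = 0.0167.

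**Step 1: one value per subject, two lenses, large-sample.** The true variance of the difference in proportions is 2p(1−p)(1−ρ)/n. The ordinary chi-square uses 2p(1−p)/n. Its real size is therefore 2[1 − Φ(1.96/√(1−ρ))], with ρ the correlation of the yes/no answers:
- ρ = 0: 5.0%
- ρ = 0.2: 2.8%
- ρ = 0.4: 1.1%
- ρ = 0.6: 0.2%

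**Step 2: one value per subject, three lenses, simulated.** 40 subjects, 40,000 trials per cell, latent normal model with a shared subject effect. The three entries in each cell are for latent correlation 0.3 / 0.5 / 0.7.

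| Coverage | Ordinary chi-square | Cochran's Q |
|---|---|---|
| Size, 90% all lenses | 2.8 / 1.8 / 0.8% | 4.7 / 4.9 / 5.1% |
| Size, 95% | 2.8 / 1.9 / 1.1% | 4.3 / 4.1 / 3.6% |
| Size, 98% | 2.2 / 1.6 / 0.8% | 2.5 / 2.0 / 1.2% |
| Power, 90/90/70% | 68 / 68 / 68% | 75 / 81 / 89% |
| Power, 90/90/80% | 21 / 19 / 16% | 28 / 32 / 39% |
| Power, 95/95/90% | 10 / 9 / 7% | 14 / 15 / 17% |
| Power, 98/98/93% | 17 / 15 / 13% | 20 / 21 / 23% |
| Power, 99/99/95% | 16 / 14 / 13% | 17 / 17 / 17% |

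At zero correlation and 90/90/70% the two tests have 67.2% and 67.7% power.

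**Step 3: both eyes as independent rows.** For two lenses, the ratio of true to assumed variance is 1 + r(two eyes, same lens) − r(same eye, different lens) − r(other eye, different lens).
- 0.8, 0.5, 0.5: ratio 0.8, size 2.8%
- 0.8, 0.4, 0.4: ratio 1.0, size 5.0%
- 0.8, 0.2, 0.2: ratio 1.4, size 9.8%

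Simulated with three lenses and latent variance shares (subject / subject-by-lens) of 0.5/0, 0.5/0.3 and 0.3/0.6, chi-square size is about 2%, 5% and 11% to 12% at 90% coverage. At 95% coverage it is about 2% to 3%, 6% and 12%. Across a wider set of shares at 70% to 90% coverage it runs from 0.9% to 13.3%.

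**Step 4: worked example.** Of 40 subjects, 29 are covered with all lenses, 2 with none, 7 uncovered only with the third, 1 only with the first and 1 only with the second. Covered totals are 37, 37 and 31, sum 105, expected 35 each.
- Ordinary chi-square = (4 + 4 + 16)/(40 × 0.875 × 0.125) = 24/4.375 = 5.49, p = 0.064.
- Cochran's Q = 2 × (3 × 3699 − 105²)/(3 × 105 − 297) = 144/18 = 8.00, p = 0.018.
- First against third lens, 7 against 1 discordant: exact McNemar p = 2 × (1 + 8)/256 = 0.070; mid-p = 0.070 − 8/256 = 0.039; ordinary chi-square p = 0.060.

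The omnibus conclusion changes. No pairwise result passes 0.0167 under any of these tests.

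**Step 5: pairwise power at 0.0167, 90% against 70%, latent correlation 0 / 0.3 / 0.5 / 0.7.**
- Ordinary chi-square: 44 / 43 / 43 / 42%
- Exact McNemar: 32 / 38 / 44 / 54%
- Mid-p McNemar: 40 / 47 / 54 / 65%

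For 95% against 90%, every pairwise test has 4% power or less.

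**The case against.** The strongest reply is that this is under-specification, not a wrong test. The chi-square family includes McNemar's test, the neighbouring methods are paired, and a competent analyst would carry the pairing over. That stands in part: the text does not prove that an unmatched test will be run. It does not exclude one either, and it leaves the unit open.

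A second reply is that the practical gain is small. All three lenses share a 14.2 diameter and have base curves of 8.5 or 8.6 (Table 1), and lenses are dispensed only if the trial fit is suitable (section 8.2.1), so coverage may be close to complete. This also stands. In the scenarios with gaps of 4 to 5 points, the matched test gains 1 to 10 points and power never exceeds 23%. The 90/90/70% case is the favourable one. In the worked example no lens pair is separated by either approach.

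A third point concerns preference. Right-against-left comfort preference and the investigator's fit preference are listed at both visits of every pair, so a subject can supply several answers. The one-sample chi-square is sound only on one answer per subject.

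A reader might infer that the ordinary chi-square is always conservative and so can create no false claim. The documents do not support that. Lenses are worn in both eyes, the unit is not stated, and with eyes pooled as independent rows the size can exceed 10%.

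**Conclusion.** The concern holds in a limited form. Section 10.1 names no matched test and no unit for nominal data in a three-period within-subject design, and the ordinary form of the named test has the wrong error rate for corneal coverage. With one value per subject and positive correlation it is conservative: size about 3% to 1% instead of 5%, and power about 68% instead of 75% to 89% at 90/90/70%. With eyes as independent rows the direction is indeterminate: size about 2% to 12%.

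These sizes rest on assumed coverage rates, correlations and variance shares with 40 subjects. Near 98% coverage Cochran's Q is itself conservative.

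A reader might also infer that the trial's main conclusion is at risk. It is not: the primary endpoint, high contrast visual acuity, does not use this test. The ordinal fit items and a one-answer preference test are not affected either.

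**What to change.** In section 10.1, replace the nominal-data clause with:

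*Matched tests for nominal data recorded for each lens: corneal coverage will be compared at each visit with Cochran's Q on one value per subject (covered in both eyes, yes/no) in subjects with all three lens values, followed by pairwise McNemar tests (mid-p), using all subjects with both values of the pair, at the multiplicity-adjusted level.*

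Keep the chi-square only as a one-sample test on one preference answer per subject, without stacking visits or lens pairs.

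A logistic GEE on both eyes, clustered on subject, should not be left as an option. It reopens the choice of unit, and it cannot be fitted when a lens has no uncovered eye. In the two-eye simulation (10,000 trials per cell) that happened in 7% to 17% of trials at 95% coverage and 48% to 66% at 98%. Its size was 4.7% to 6.9%, against 4.5% to 5.0% for Q on the both-eyes value at 90% to 95% coverage.

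The cost is wording only: coverage is already recorded at both visits for every pair, so no subjects, visits or measurements are added. There are three downsides. Q omits subjects missing a lens, although the pairwise tests keep those with both values of the pair. Combining the eyes gives up some eye-level information. Mid-p McNemar may lose a few points of power if within-subject correlation is near zero (40% against 44% in step 5).

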CooperVision

FINAL

Fitting Evaluation of Hydrogel and Silicone Hydrogel Sphere Design Contact Lenses.

Sponsor Study Code: EX-MKTG-79
Protocol Date: January, 2017
Sponsor Company: CooperVision, Inc.
Document Type: Protocol
Study Category: Post Market
Start Date: February, 2017
Finish Date: March - April, 2017
Clinical Site: School of Optometry Clinic, National Autonomous University (UNAM), Mexico City

Protocol Sponsor: [REDACTED]

Site Principal Investigator: [REDACTED]

Revision History

Document number	Date	Comments
EX-MKTG-79	1/12/2017	First draft (v 1.0)
EX-MKTG-79	1/13/2017	Second draft (v 2.0)
EX-MKTG-79	1/13/2017	Final

Confidential

EX-MKTG-79 Fitting Evaluation of Hydrogel and Silicone Hydrogel Sphere Design Contact Lenses.

PERSONNEL & FACILITIES

STUDY SPONSOR: CooperVision Inc.
[name]
[name]

SPONSOR COORDINATOR: [REDACTED]
[REDACTED]
[REDACTED]
[REDACTED]

SITE PRINCIPAL
INVESTIGATOR: [REDACTED]
[REDACTED]
[REDACTED]
[REDACTED]

STATISTICAL ADVISOR: [REDACTED]
[REDACTED]
[REDACTED]
[REDACTED]

STUDY MONITOR: [REDACTED]
[REDACTED]
[REDACTED]
[REDACTED]

Protocol Synopsis

Protocol Number	EX-MKTG-79
Title	Fitting Evaluation of Hydrogel and Silicone Hydrogel Sphere Design Contact Lenses.
Name of Device(s) and (by USAN material)	Biomedics XC (omafilcon A), Proclear (omafilcon A), Clariti® elite (somofilcon A)
Indications for Use	
Approved for use:
 
 • omafilcon A (Daily wear, monthly replacement) • somofilcon A (Daily wear, monthly replacement) 
Indication for use in this study:
 
 • daily wear for all lens types
Study Design	Prospective, non-dispensing, double masked, randomized, bilateral, daily wear in each study pair.
Purpose	The aim of this non-dispensing fitting study is to evaluate the short term lens fit, vision performance and patient subjective experiences of three monthly replacement sphere lenses.
Study Duration	
The anticipated timeline for this study is as follows:
 
 • Patient enrolment: February- March, 2016 • Visits: V1 (Dispensing), V2 (1 hour post lens settling) for each lens pair.
Patient Population	Habitual soft contact lens wearers with myopia that provide written informed consent and meet the protocol entrance criteria.
Sample Size	Target enrollment and completion is 40 subjects total.

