The aim of this non-dispensing study is to evaluate the short term lens fit, vision performance and patient subjective experiences of three monthly replacement sphere lenses.

The key variables of interest are:

- High contrast distance visual acuity
- Lens fitting characteristics and preference
- Subjective comfort ratings and preference
- Subjective handling ratings and preference (insertion & removal assessed by subjects)

** Lens fit preference judged by the study investigator*

3 Study Hypothesis

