8.1 Participants

Adapted soft contact lens wearers with myopia will be recruited for the study for a minimum of **40** completed. Subjects will be recruited from the National Autonomous University School of Optometry databases who agree to voluntarily participate in the study (Appendix 2, timeline). All subjects will be screened to determine study eligibility. Each subject will be given a unique ID number. Additionally, all subjects must meet the study inclusion and exclusion criteria listed below.

Inclusion criteria

A person is eligible for inclusion in the study if he/she:

- Is between 18 and 40 years of age (inclusive).
- Has had a self-reported visual exam in the last two years.
- Is an adapted soft CL wearer who is not wearing any of the study lenses.

- Has a CL spherical prescription between - 1.00 and - 6.00 (inclusive)
- Has a spectacle cylinder up to 0.75D in each eye.
- Can achieve best corrected spectacle distance visual acuity of 20/25 (0.10 logMAR) or better in each eye.
- Can achieve a distance visual acuity of 20/30 (0.18 logMAR) or better in each eye with the study contact lenses.
- Has clear corneas and no active ocular disease.
- Has read, understood and signed the information consent letter.
- Patient contact lens refraction should fit within the available parameters of the study lenses.
- Is willing to comply with the wear schedule.
- Is willing to comply with the visit schedule.

Exclusion Criteria

A person will be excluded from the study if he/she:

- Has never worn contact lenses before.
- Currently wears rigid gas permeable contact lenses.
- Has a history of not achieving comfortable CL wear (5 days per week; > 8 hours/day)
- Has a CL prescription outside the range of - 1.00 to - 6.00D
- Has a spectacle cylinder \geq 1.00D of cylinder in either eye.
- Has contact lens best corrected distance vision worse than 20/25 (0.10 logMAR) in either eye.
- Presence of clinically significant (grade 2-4) anterior segment abnormalities.
- Presence of ocular or systemic disease or need of medications which might interfere with contact lens wear.
- Slit lamp findings that would contraindicate contact lens wear such as:
 - Pathological dry eye or associated findings
 - Pterygium, pinguecula, or corneal scars within the visual axis
 - Neovascularization > 0.75 mm in front of the limbus
 - Giant papillary conjunctivitis (GCP) worse than grade 1
 - Anterior uveitis or iritis (past or present)
 - Seborrheic eczema, Seborrheic conjunctivitis

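### Does the 80% power claim in section 10.1 need rewriting because the SD, the alpha behind the 33, the adjustment method and the family of tests are not stated?

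*Combined protocol and SAP*

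**What the plan says.** The primary endpoint in the Protocol Synopsis is "High contrast visual acuity". Section 3.1 gives a non-directional alternative: "There is a difference in high contrast visual acuity, lens fitting characteristics and subjective assessments between lens types". Section 2 names three lenses, and sections 4 and 8.3 have every subject wear all three, so there are three pairwise contrasts. Section 8.3.1 records HCVA both monocularly and binocularly.

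Section 10.1 holds all of the statistical text. On the test it says: "Differences between lenses will be compared using Paired t-tests". The next sentence allows paired t-tests or analysis of variance for continuous data. On size it says: "A sample size of 33 subjects was calculated which provides 80% power to detect a difference of half a line in logMAR" HCVA. The significance level is 0.05, "with adjustment for multiple comparisons".

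The planned number is larger than the 33. The Synopsis says "Target enrollment and completion is 40 subjects total", and section 8.1 says subjects "will be recruited for the study for a minimum of 40 completed".

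**The concern.** A power statement can be checked only if its inputs are given. For a paired t-test these are the difference, the SD of the paired differences, the alpha, the sidedness and the number of subjects. Section 10.1 gives the difference, the number and a nominal 0.05. It mentions a standard deviation only as an example of a summary statistic. It does not say whether the 33 was worked out before or after the multiplicity adjustment, how that adjustment is made, or over which tests.

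Two things appear to be at stake. First, if the 33 was found at an unadjusted 0.05 and the tests are then judged at a stricter level, power for each lens pair would be below what a reader takes from the sentence. Secondly, an unnamed family could be settled after the data are seen. With Bonferroni, a raw p of 0.01 becomes 3 × 0.01 = 0.03 over three tests, but 9 × 0.01 = 0.09 over nine (three lens pairs, each tested for the right eye, the left eye and binocularly).

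**Working it through.** **Inputs from the protocol.** n = 33, power 80%, a difference of half a line, nominal alpha 0.05 and paired t-tests (section 10.1); three lenses (section 2); 40 completers (Synopsis, section 8.1); a non-directional alternative (section 3.1).

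**Assumptions.** One line is 0.10 logMAR, so δ = 0.05. Tests are two-sided unless noted. Bonferroni over three pairs (0.05/3 = 0.0167 each) is the example adjustment.

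**Formula.** Power = P(T > t₁₋α/₂,ₙ₋₁), where T is noncentral t with n − 1 degrees of freedom and noncentrality δ√n/SD.

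**Step 1: the plan's own figure.** Without an SD the 33 cannot be reproduced forwards. It can be solved backwards for the SD that gives 80% power at n = 33. At two-sided 0.05 the SD is 0.0994 (noncentrality 0.05 × √33 / 0.0994 = 2.89). At two-sided 0.05/3 it is 0.0848 (noncentrality 3.39). Each alpha fits the 33 with its own SD, so the protocol does not reveal which was used and is inconsistent with none of them.

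**Step 2: power at 40 completers, each pair tested at 0.05/3.** For SD 0.0994 the noncentrality is 0.05 × √40 / 0.0994 = 3.18 and the critical t on 39 df is 2.50, giving power 0.748. The other rows follow in the same way.

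| Alpha behind the 33 | Implied SD | Power per pair at 40 |
|---|---|---|
| two-sided 0.05 | 0.0994 | 75% |
| two-sided 0.025 | 0.0895 | 84% |
| two-sided 0.05/3 | 0.0848 | 88% |
| two-sided 0.05/9 | 0.0746 | 95% |
| one-sided 0.05 | 0.1130 | 62% |

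The last row sits badly with the non-directional alternative in section 3.1. Without it the range is 75% to 95%. At 40 completers, 80% per pair holds for any SD up to 0.094.

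**Step 3: other permitted methods in the weakest two-sided case.** Simulation at SD 0.0994 and n = 40, with equal correlations, one pair differing by 0.05 and the third lens between the other two or equal to one of them, gives power for that pair of:

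- 75% with Bonferroni;
- between 76% and 79% with Holm;
- 79% to 85% with an analysis-of-variance test followed by paired tests at 0.05.

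The last route is open because section 10.1 names analysis of variance as an option.

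**Step 4: the nine-test family.** At 0.05/9 and n = 40, power is 60% for SD 0.0994 and 78% for SD 0.0848. But section 8.3.1 only lists what is recorded. No section plans separate right-eye, left-eye and binocular primary tests, so these figures describe a family that the protocol does not set up.

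**The case for a change.** The strongest case for a change is that the sponsor must have had an SD and an alpha to arrive at 33, so stating them costs one sentence. An unadjusted two-sided 0.05 is an ordinary reading of section 10.1. On that reading, 40 completers with Bonferroni give 75%, and 80% would need 45. Section 10.1 points to no appendix for these inputs, and the sentences there are complete rather than redacted. Because the results bear on moving Biomedics XC wearers to one of two successor lenses, which pairs are declared different is the practical output, and a family fixed in advance would protect it.

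Much of this stands. The inputs are missing, and naming them, together with the primary HCVA measure (monocular or binocular), would be better reporting. It does not show an error, however. The 33 is attainable at an SD of about 0.10 with an unadjusted alpha, or about 0.085 with an adjusted one. The plan commits in advance to a multiplicity adjustment, so it does not license unadjusted testing. Naming Bonferroni would choose one acceptable method among several, and usually the least powerful of them. The p-value example needs the nine-test family, which is hypothetical.

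**Conclusion.** No change is needed. Section 10.1 leaves out details that would let a reader verify the 80%, but it contains no wrong rule and no figure shown to be false. Three lens pairs, two-sided tests and a standard adjustment are the natural reading of what is already written, and an analyst would fill the gap that way.

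On that reading, power per pair at 40 completers runs from about 75% (33 found at unadjusted 0.05) to about 88% (33 found at 0.05/3). In the first case the shortfall is five points with Bonferroni, and smaller or absent with Holm or an analysis-of-variance approach. The seven completers beyond the 33 absorb much of the cost of adjustment: at SD 0.0994 and 0.05/3, power is 64% with 33 and 75% with 40. These figures assume 0.10 logMAR per line and SDs inferred from the 33, because the protocol states neither. In a one-hour fitting study of marketed lenses, an uncertainty of this size about power does not change the design, the number recruited or the analysis.
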